1.2 STUDY OVERVIEW

StatinWISE trial is a series of N of 1 double-blinded placebo controlled trials to determine whether the muscle symptoms attributed to statin use by patients are caused by statins. Two hundred adults who have either stopped, or are considering stopping, statin treatment due to muscle symptoms will be allocated a randomised sequence of 6 treatment periods, comprising 3 placebo and 3 atorvastatin periods. Each treatment period will last two months.

Randomisation and baseline data: Eligible and consenting patients should be randomised as soon as possible, and the study treatment started within 4 weeks of randomization. The Baseline Data form (Appendix 1), completed directly via the online trial database by the Research Nurse at the screening visit, will be used to assess eligibility and collect baseline patient information.

Follow-up: At the end of each two-month treatment period, patients will be asked to complete the Patient Questionnaire (Appendix 2). During the last week of each two-month treatment period, patients will also be asked to complete daily VAS Pain Scale forms. Outcome collection will be by a method chosen by the patient at the screening visit: via a bespoke mobile app, the website, paper or by telephone to trial staff.

At month 15, trial staff will telephone the patient to document their decision on future statin use and whether their results helped reach this decision. This will be the last data collection point of the trial.

In the two-monthly questionnaire, patients will be asked to self-report any event which resulted in unplanned hospital admissions. Where a patient indicates that there was an unplanned admission, the GP/Research Nurse will be asked to submit a brief report to the Trial Coordinating Team and where the event is believed to be unexpected and associated with statin use, an Adverse Event Report Form will be completed. Participating GPs will also report any event to the trial team which results in unplanned hospital admissions, patient death or where a patient has a baby with any congenital anomaly/birth defect within 24 hours of becoming aware of the event. To minimize the risk of unreported events, at two-monthly intervals, the Research Nurse/GP will conduct a search of their database for any StatinWISE patients who have been recorded as having died. The GP/Research Nurse will be asked to submit a brief report to the Trial Coordinating Team and where the event is believed to be unexpected and associated with statin use, an Adverse Event Report Form will be completed

1.3 PATIENT POPULATION

Two hundred adults with a clinical indication for statins who have either stopped, or are considering stopping, statin treatment due to muscle symptoms. There is no limit to the maximum number of patients to be recruited at each GP.

General Practitioner (GP) Practices will be recruited through the Clinical Research Network across England and Wales; practices will continue to be added until the sample size is achieved. Suitable collaborating practices and investigators will be assessed on their ability to conduct a trial. In advance of the trial starting at a practice, the Principal Investigator must agree to follow Good Clinical Practice Guidelines and all relevant regulations. All relevant regulatory and ethics approvals must be in place prior to practices recruiting their first patient.

1.4 ELIGIBILITY

Inclusion criteria:

- Adults (aged 16 and over)
- Registered in a participating GP practice
- Previously prescribed statin treatment in the last 3 years
- Stopped OR is considering stopping statin treatment due to muscle symptoms
- Provided fully informed consent

Exclusion criteria:

- Any previously documented serum creatine kinase (CK) levels at or above three times the upper limit of normal;
- Taken statins in the previous week and has an increase in serum alanine aminotransferase (ALT) at or above three times the upper limit of normal;
- Any contraindications listed in the Summary of Product Characteristics for Atorvastatin 20 mg (Appendix 3)

- Should not participate in the trial in the opinion of the general practitioner.

1.5 BLINDING AND UNBLINDING

Blinding will be achieved through the use of matching placebo.

Access to the interim data and results will be limited to members of the Data Monitoring Committee (DMC) and their externally based, independent DMC statistician who will be in charge of quality assuring the interim analyses and writing the reports.

In general, there should be no need to unblind the allocated treatment during the treatment phase. If some contraindication to statins develops after randomisation, the trial treatment can be stopped and all usual standard care given. Unblinding should be done only in those rare cases where the clinician believes that clinical management depends importantly upon knowledge of whether the patient is receiving statin or placebo. In those few cases when urgent unblinding is considered necessary, a 24-hour telephone service will be provided by the CTU and details provided in the Investigator's Study File and the Patient Alert Card. The caller will be told whether the patient is receiving statin or placebo. An unblinding report form will be completed by the person requesting the unblinding. Participation will not restart once unblinding has occurred.

1.6 OBJECTIVES

The StatinWISE trial will provide reliable evidence as to whether the muscle symptoms attributed to statin use by patients are caused by statins.

1.7 DEFINITION OF PRIMARY OUTCOME

The primary outcome is patient reported muscle symptoms (pain, weakness, tenderness, stiffness or cramp to the body), on a Visual Analogue Scale (VAS), with possibly responses ranging from 0 to 10. This will be collected daily via the VAS Pain Scale data form (Appendix 1) during the last 7 days of each of the 6 treatment periods via the patient's nominated collection method (app, website, phone call, or paper form).

1.8 DEFINITION OF SECONDARY OUTCOMES

The following secondary outcomes will be collected once at the end of each of the 6 treatment periods, via the patient questionnaire form (Appendix 2).

- Whether or not the patient experienced muscle symptoms that they believe were caused by the study medication (yes/no/don't know).
- Site of muscle symptoms:
 - Single/multiple
 - head and neck/upper limbs/lower limbs/trunk
- Visual Analogue Scale scores (range 0-10) for how the participant's muscle symptoms impact on the following:
 - General activity
 - Mood
 - Walking ability
 - Normal work (includes both work outside the home and housework)
 - Relations with other people
 - Sleep
 - Enjoyment of life

These are collected only if the participant reports muscle symptoms during that period. For comparisons between randomized treatments these VAS scores will be set to zero for participants who report no muscle symptoms in that period.

- Other symptoms that the patient believes can be attributed to the study medication. These will be entered as free text and grouped into: musculoskeletal/gastrointestinal/respiratory/neurological/psychological/other (not mutually exclusive categories).
- Adherence to study medication:
 - not at all/some days/most days/every day

Adherence will also be assessed in the following ways:

- number of pills remaining in returned packages (0-56; collected each treatment period)
- self-report ("took pill yesterday" - yes/no; collected daily during the last 7 days of each of the 6 treatment periods)

The final secondary outcomes will be collected in the end of trial interview with the participant:

- Participant decision regarding future statin use and the relationship to their primary outcome (patient has been given a statin prescription in 4 weeks following trial - yes/no).
- Whether patients found their own trial result helpful in making the decision about future statin use (yes/no).

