BACKGROUND: Statins are the most commonly prescribed treatment in the UK. Recently updated NICE guidelines have lowered the threshold for statin use to include all patients with a 10% or greater 10-year risk of cardiovascular disease. Previous randomised trials have established the prevalence of serious adverse effects of statins such as rhabdomyolysis, however, many patients discontinue statins due to less severe symptoms, such as muscle pain or fatigue. Randomised trials have shown no differences between those taking statin and placebo in terms of the prevalence of these side effects (approximately 9%), but currently there is no pathway of care for clinicians to empirically and objectively evaluate whether symptoms reported by a statin-user are caused by the statin itself or the so-called 'nocebo' effect (symptoms reflecting patient expectation of side effects). Given the effectiveness of statins in preventing cardiovascular disease, accurate data on the cause of symptoms experienced during statin use are needed to reliably inform patient and clinician about continuation of use. The proposed StatinWISE trial will provide definitive answers to this important uncertainty about statin therapy.

AIM: To determine whether statins cause muscle symptoms.

PRIMARY OUTCOME: Patient reported muscle symptoms (pain, weakness, tenderness, stiffness or cramp).

SECONDARY OUTCOME: Relationship between individual trial result and patient decision whether to continue statins long term.

TRIAL DESIGN: A series of randomised, double-blinded N-of-1 trials.

DIAGNOSIS AND INCLUSION/EXCLUSION CRITERIA:

Inclusion criteria:

- Adults (aged 16 and over)
- Prescribed statin treatment in the last 3 years
- Stopped OR considering stopping statin treatment due to muscle symptoms
- Provided fully informed consent.

Exclusion criteria:

- Any previously documented serum alanine aminotransferase (ALT) levels at or above three times the upper limit of normal;

- Have persistent, generalised, unexplained muscle pain (whether associated or not with statin use) and have creatinine kinase (CK) levels greater than 5 times the upper limit of normal
- Any contraindications listed in the Summary of Product Characteristics for Atorvastatin 20 mg (Appendix 8)
- Should not be using atorvastatin 20mg daily in the opinion of the general practitioner.

TEST PRODUCT, REFERENCE THERAPY, DOSE AND MODE OF ADMINISTRATION: Once daily oral atorvastatin 20mg or placebo for 12 months.

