We are working closely with the Cholesterol Treatment Trialists’ Collaboration performing a meta-analysis of statin adverse events reported in RCTs of statins, which will determine using individual participant data whether there is an excess of adverse events among those allocated statin compared with placebo, and whether to date there has been any bias in the reporting of adverse events in statin trials. However, for the reasons outlined above, re-analysis of the existing evidence may not alleviate individual patient concerns.

Despite evidence-based recommendations about the risks and benefits of statin use, many patients believe their symptoms are due to statins, leading to discontinuation, and are therefore potentially

missing out needlessly on an effective drug intervention. General Practitioners (GPs) are faced with the challenge of decision making when patients present with symptoms during statin use as there is currently no diagnostic tool allowing clinicians to empirically evaluate whether symptoms reported by an individual statin user are caused by the statin itself or by the 'nocebo' effect.

N-of-1 trials offer the opportunity for individual patients to discover whether the symptoms that they are experiencing are attributable to statins. Each patient acts as their own control, and therefore their optimal treatment can be established.^{16, 17} Importantly, N-of-1 trials offer individual patients the opportunity to observe their own response to active and placebo treatments. We anticipate that this knowledge will be an important determinant of subsequent statin use and therefore we will follow patients for three months after their blinded treatment period has ended. At the end of these three months we will be able to ascertain as to whether they are using statins.

The proposed trial will address some of the criticisms of previous evidence. The trial will be blinded and placebo-controlled to minimise bias and the sequence of statin and placebo treatments will be randomised to avoid confounding. Additionally, the within-patient comparisons of symptoms experienced while on placebo and statins will allow us to determine, definitively: (i) whether individual patient symptoms are caused by statins and (ii) the extent to which symptoms attributed to statins appear to be causally related.

2. Trial design

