2.10.3 END OF TRIAL DATA

During the seventh week of treatment period 6, the Research Nurse will contact patients to thank them for their participation so far, inform them that this is the last treatment period, and that they, together with their GP, will receive their individual results at the beginning of month 14. The Research Nurse and patient will arrange a telephone or face-to-face appointment to discuss the individual results during month 14. The Research Nurse will also inform patients that if they want to continue taking a statin without a break, to arrange a separate clinical appointment with their GP prior to the end of the treatment period.

At month 15, trial staff will email/telephone the patient to document their decision on future statin use and whether their results helped reach this decision. This will be the last data collection point of the trial.

Throughout the trial, continued patient care will be at the discretion of their GP. In primary care, the patient will be recorded as having an ongoing statin prescription.

- Where treatment with an interacting drug is needed that will be for less than one-month duration, the patient will be asked to stop the trial treatment for that period.
- Where treatment with an interacting drug is needed for longer than one month, the patient will be asked to withdraw from study treatment completely.

When the patient is randomised, a temporary Read code indicating StatinWISE participation will be recorded in their primary care record, the code will be removed at the end of the trial.

Patients will also be given an alert card that identifies them as a StatinWISE patient. Patients will be asked to present this card to anyone providing medical care outside of their usual general practice. This card will have a link to the trial website and a trial contact number.

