2.16 END OF TRIAL FOR PARTICIPANTS

The follow-up period ends 15 months after the first treatment day with a final contact (telephone or face-to-face) with the Research Nurse as described above. This will be considered as the end of trial for patients.

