Appendix 3: StatinWISE End of Trial data form

End of Trial Form (Month 15) / Early Withdrawal

1. Did the patient complete 6 Treatment Periods?

YES

A.1. Has the Research Nurse/GP spoken to the patient to discuss their individual results?

(i) YES

(ia) Date seen: _____ dd/mm/yyyy

(ii) NO – (please arrange an appointment).

(iia) Date of appointment: _____ dd/mm/yyyy

A.2. Has the patient seen his/her GP since end of Treatment Period 6?

(i) YES

(ii) NO (please remind the patient to book an appointment)

(iia) Date reminder done: _____ dd/mm/yyyy

A.3. Has the patient been given a statin prescription in the 4 weeks since Treatment Period 6 ended?

(i) YES

(ia) Name of Statin: _____

(ib) Dose of statin: _____

(ii) NO

A.4. Has the patient found their own trial results helpful to reach the decision as to whether to continue statin use?

YES/NO

NO

B.1. Please tick reason why the patient did not complete 6 treatment periods:

Lost to follow-up

Early withdrawal

Death

B.2. Lost to follow-up:

Date of last contact with patient? _____

Dd/mm/yyyy

B.3. If Early withdrawal, give reason:

- a. withdrawal of informed consent
- b. intolerable muscle symptoms*
- c. clinical concern*
- d. other*

*: please enter details here: _____

B.4. Has the patient contacted their GP to discuss reason for withdrawal?

(i) YES

(ia) Date seen: _____ dd/mm/yyyy

(ii) NO – (advise patient to contact GP).

B.5. Has the Research Nurse/GP spoken to the patient to discuss their individual results?

(i) YES

(ia) Date seen: _____ dd/mm/yyyy

(ii) NO – (please arrange an appointment).

(iia) Date of appointment: _____ dd/mm/yyyy

B.6. Death (SAE report form must be completed)

B.6.a. Date of death: _____ dd/mm/yyyy

B.6.b Cause of death (either autopsy report or clinical judgement if autopsy not available):

B.6.c. Date SAE form completed: _____ dd/mm/yyyy

C.1. This form was completed by: _____ Date: dd/mm/yyyy

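### The decision on future statin use is due at month 15, after results, but the only form item for it covers 4 weeks that nominally end before or just as results arrive

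*SAP*

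**What the plan says.** The protocol synopsis gives as its secondary outcome "Relationship between individual trial result and patient decision whether to continue statins long term". Protocol 2.13 lists the same question among seven secondary outcomes.

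The timetable is in Protocol 2.10.3. Patients are told that "they, together with their GP, will receive their individual results at the beginning of month 14", and the results are discussed with the Research Nurse during that month. Then: "At month 15, trial staff will email/telephone the patient to document their decision on future statin use". The same section adds: "This will be the last data collection point of the trial". SAP 1.2 agrees on month 15. Protocol section 1 gives the purpose of the three-month follow-up: "At the end of these three months we will be able to ascertain as to whether they are using statins".

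The recorded variable is narrower. The End of Trial form (Protocol Appendix 3) is headed Month 15, and its item A.3 asks: "Has the patient been given a statin prescription in the 4 weeks since Treatment Period 6 ended". Item A.4 asks whether the results helped, not what was decided. No item asks for the decision or for current statin use. SAP 1.8 defines the outcome as "patient has been given a statin prescription in 4 weeks following trial - yes/no" and says it is collected at the end-of-trial interview. SAP 2.3.2 relates the decision to each patient's estimated statin effect.

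**The concern.** The question is whether seeing one's own result goes with a different decision about statins. To address it, the decision must be observed after the result has been seen. A.3 looks back to the weeks straight after treatment, when on the planned timetable the patient is still waiting for the result.

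Any association found with A.3 would then mostly reflect what the patient believed before disclosure. Patients whose minds were changed by the result, who are the ones of interest, would be coded by their earlier position. An unrecorded decision cannot be recovered later by rewording the SAP.

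**Working it through.** **Inputs.**
- Treatment period 6 occupies months 11 to 12 (Protocol Appendix 1).
- Each period is exactly 56 days (SAP 2.3.1).
- Results come at the beginning of month 14 (Protocol 2.10.3), taken here as 13 completed months.
- Final contact: "The follow-up period ends 15 months after the first treatment day with a final contact" (Protocol 2.16).
- The documents do not define a month in days, so I used 28 days (half a 56-day period) and 30.44 days (365.25 / 12).

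**Item A.3 against the release of results**, in days from the first treatment day, with no breaks:

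| Step | 28-day months | Calendar months |
|---|---|---|
| End of period 6 | 6 x 56 = 336 | 12 x 30.44 = 365.3 |
| A.3 window closes (+28) | 364 | 393.3 |
| Results released | 13 x 28 = 364 | 13 x 30.44 = 395.7 |
| Gap, window close to results | 0 | 2.4 |
| Final contact at 15 months | 420 | 456.6 |
| Results to final contact | 56 | 60.9 |
| Part of that covered by A.3 | 0 | 0 |

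If the contact is made at the start of month 15 on 28-day months, the time from results to contact is 14 x 28 - 13 x 28 = 28 days. The interval in which an informed decision could be seen is therefore about 28 to 61 days. A.3 covers none of it on the nominal schedule.

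**Effect of breaks.** Protocol 2.9.3 allows breaks between periods and sets no limit on them. Assume a break delays the end of period 6 while the results date stays fixed. A total break of 14 days then gives an overlap of 14 days (28-day months) or 14 - 2.4 = 11.6 days (calendar months). A break of 28 days gives 28 or 25.6 days. If the results date moves with the end of treatment, the overlap stays at zero.

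**SAP 1.8.** The phrase has two readings.
- *Following treatment:* this is the A.3 window again, with the same result.
- *Following the end of trial as Protocol 2.16 sets it:* the window opens at the final contact, so none of it has been observed at the interview that is meant to collect it.

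Neither reading captures the time between results and the last contact.

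**How A.3 codes patients on the nominal schedule:**

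| Patient | Position at month 15 | A.3 |
|---|---|---|
| Prescribed in the 4 weeks, continues | on statin | yes |
| Not prescribed, stays off | off statin | no |
| Starts because of the result | on statin | no |
| Prescribed in the 4 weeks, stops after the result | off statin | yes |

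A.3 agrees with the month-15 position only where the result changed nothing. Both kinds of change are coded the wrong way.

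**Could the decision be stored elsewhere?** Protocol 2.10 limits the trial database to what is on the listed forms. The SAP text cites no end-of-trial form of its own, so Protocol Appendix 3 is the only one supplied.

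**The case against.** **The gap is tiny.** A difference of 0 to about 2 days is a boundary effect on a nominal calendar, and small slippage would produce overlap. This stands as a limit on the claim: A.3 largely misses informed decisions, not necessarily all of them. But any overlap would depend on the patient's breaks, so the variable would mean different things for different patients.

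**A reader might infer a gap of about a month.** Pairing 56-day periods with calendar months gives 395.7 - 364 = 31.7 days. No passage states that pairing. It also puts the end of period 6 at 336 / 30.44 = 11.04 months, which does not fit Appendix 1, where period 6 fills months 11 to 12.

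**A reader might infer that the form and the SAP use two different windows.** The documents do not establish this. SAP 1.8 collects its variable at the interview and shares A.3's content and 4-week length, so it is most naturally a loose paraphrase of A.3. On the literal reading the window does differ, but it then lies wholly after results. Its fault would be that it cannot be observed, not that it comes too early.

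**A prescription is a fair proxy, and staff will ask about the decision anyway.** A prescription is concrete, and Protocol section 1 itself speaks of statin use, so recording prescribing is reasonable. The fault is its timing. Staff may well ask, but no supplied form has a place for the answer.

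**The consequence is limited.** That is correct. SAP 2.3.2 names no model or test for this analysis. Even a well-timed variable would give an association, not the causal effect of disclosing results.

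**Conclusion.** The point holds. The protocol and SAP promise a decision recorded at month 15, after results. The only matching form item covers 4 weeks that close 0 to about 2 days before results on the nominal schedule, and SAP 1.8 either repeats that window or describes one not yet observable. The analysis relating the decision to the individual statin effect would largely miss decisions informed by the result.

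This rests on three assumptions: month 14 begins after 13 completed months, a month is 28 or 30.44 days, and there are no breaks in treatment. Breaks could give partial overlap.

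The primary outcome and its analysis are untouched. The documents give no rate at which patients change course after results, so no count of misclassified patients can be given. It should be fixed, because this is the secondary outcome that the synopsis singles out.

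**What to change.** At the month-15 contact already scheduled, add two dated items to Section A of the End of Trial form:
1. the patient's stated decision on future statin use;
2. whether a statin has been prescribed or is in use since results were given.

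Record the date results were received as well; A.1 already has a date for the discussion. Define the SAP 1.8 outcome from these items, say which one enters the SAP 2.3.2 analysis, and use the same wording in the SAP and on the form. Keep A.3 only as a description of prescribing before results.

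Two minor additions:
- Section B (patients who did not complete six periods) has no decision or prescription item, although B.5 records discussion of results. Ask the same two items of those who have had that discussion and can be contacted.
- State whether A.3 counts a prescription issued just before period 6 ended. Protocol 2.10.3 makes such prescriptions likely, because patients who want no break are told to see their GP by then.

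The cost is a small form amendment and one SAP definition. SAP section 1 allows the SAP to change before database lock, but that does not cover the protocol form. No extra contact is needed for patients who have not reached month 15. Those already past it keep only the old item, so report how many patients have each version.
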